Subjects who enroll directly into SP848 without previous participation in a LCM clinical study will undergo screening. Eligible subjects will initiate treatment with LCM, and the LCM dose will be titrated to a level to optimize tolerability and seizure control (see Section 4.4.1). Subjects will be able to receive LCM oral solution or LCM tablets for up to 2 years as determined appropriate by the investigator.

The same study conditions described in Section 4.1.1 (eg, minimum and maximum LCM dose, required office visits for dose increases, concomitant AEDs, and study medication taper) also apply.

*Clinical Study Protocol, Section 4.2.1 (Primary variables). The following variables were added:*

- Achenbach CBCL at Baseline for children 18 months and older (CBCL/1½-5 and CBCL/6-18) assessing behavior

- Bayley-III scales at Baseline for children <18 months of age at time of enrollment (applicable only to subjects enrolled in English-speaking countries)

*Clinical Study Protocol, Section 4.2.2 (Secondary variables). Original text:*

Secondary efficacy variables include:

- Seizure counts, which will be assessed using seizure diaries in order to evaluate preliminary evidence of efficacy during long-term exposure in this population
- Clinical Global Impression of Change
- Caregiver Global Impression of Change

*Was revised as follows:*

Secondary variables include:

- Seizure counts, which will be assessed using seizure diaries in order to evaluate preliminary evidence of efficacy during long-term exposure in this population
- Clinical Global Impression of Change
- Caregiver Global Impression of Change
- LCM palatability and ease of use questionnaire

*Clinical Study Protocol, Section 4.3.1 (Inclusion criteria). Original text:*

Subjects must fulfill the following inclusion criteria:

1. A signed informed consent form has been obtained from the parent/legal guardian and assent has been obtained from the subject (when possible or as required according to local Institutional Review Boards [IRBs]/Independent Ethics Committees [IECs]).
2. Subject has completed SP847 (or the subject discontinued SP847 due to a dose reduction or status epilepticus) for the treatment of uncontrolled partial-onset seizures, or subject has participated in other LCM pediatric clinical studies in epilepsy.
3. Subject is expected to benefit from participation, in the opinion of the investigator.

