### **Recommended LCM dose titration for subjects enrolling directly into SP848**

Formulation	Week 1	Week 2	Week 3	Week 4	Week 5	Week 6
Oral solution (syrup)	2mg/kg/day (1mg/kg bid)	4mg/kg/day (2mg/kg bid)	6mg/kg/day (3mg/kg bid)	8mg/kg/day (4mg/kg bid)	10mg/kg/day (5mg/kg bid)	12mg/kg/day (6mg/kg bid)
Tablet	100mg/day (50mg bid)	200mg/day (100mg bid)	300mg/day (150mg bid)	400mg/day (200mg bid)	500mg/day (250mg bid)	600mg/day (300mg bid)

bid=twice daily; LCM=lacosamide

The investigator, together with the subject/caregiver (including parent/legal guardian), will be able to choose either the oral solution (syrup) formulation or the tablet formulation of LCM in this study. The study medication will be orally administered bid (at 12-hour intervals, once in the morning and once in the evening) in equally divided doses. The oral solution (syrup) formulation will be measured and orally administered via a dosing syringe. The selection of doses, titration

scheme, and rate of taper in SP847 were based on adult studies and were adjusted to a mg/kg basis plus 40% (ie, 600mg/day adult dose of LCM corresponds to [600mg/70kg] x 1.4 = approximately 12mg/kg/day for a child). The selection of doses in this trial is based on the maximum recommended dose in SP847.

The investigator may adjust the LCM dose to a minimum of 2mg/kg/day (oral solution [syrup]) or 100mg/day (tablet) and a maximum of 12mg/kg/day (oral solution [syrup]) or the corresponding dose levels for the tablet formulation) not to exceed 600mg/day based on body weight, even if the subject's body weight exceeds 50kg. The maximum permitted LCM dose in SP848 is 12mg/kg/day or 600mg/day, whichever is lower.

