The investigator may increase the dose of LCM no faster than 2mg/kg/day (oral solution [syrup]) or 100mg/day (tablet) per week to a maximum of 12mg/kg/day (oral solution [syrup]) or the corresponding dose levels for the tablet formulation) not to exceed 600mg/day based on body weight, even if the subject's body weight exceeds 50kg. The maximum permitted LCM dose in SP848 is 12mg/kg/day or 600mg/day, whichever is lower. The investigator may decrease the dose of LCM to a minimum of 2mg/kg/day (oral solution [syrup]) or the corresponding dose level for the tablet formulation). Increases in the LCM dose must occur only during office visits. It should be noted, in cases of incomplete doses (eg, subject spits out all or a portion of the syrup), missed doses, or administration of an erroneous volume of syrup, study medication should not be readministered and these subjects would remain at their assigned dose.

Subjects enrolling from SP847 will have the option of remaining on the oral solution formulation of LCM or switching to the commercial tablet formulation, if feasible. Consideration of the current LCM milligram dose in the oral solution (syrup) should occur if/when transitioning to the tablet formulation. In cases where the LCM dose received with the oral solution (syrup) is not supported by the tablet strengths available in SP848 (50mg and 100mg), a clinical decision must be made by the investigator or other study physician to either increase or decrease the LCM dose to the next multiple of 100mg with a maximum permitted dose of 600mg/day.

Subjects achieving a dose of LCM  $\geq$ 6mg/kg/day (oral solution [syrup]) or  $\geq$ 300mg/day (tablet) who withdraw during the study should taper off study medication. It is recommended that the dose be tapered gradually in weekly decrements of 4mg/kg/day (oral solution [syrup]) or 200mg/day (tablet) (see tables below). A slower taper of 2mg/kg/day (oral solution [syrup]) or 100mg/day (tablet) is permitted, if medically necessary. In case of an emergency, a faster taper is permitted after discussion with the medical monitor, whenever possible.

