### **Recommended LCM dose reduction (taper) for oral solution (syrup) formulation**

Maximum LCM dose achieved a	Taper schedule		
	Week 1	Week 2	Week 3
12mg/kg/day (6mg/kg bid)	8mg/kg/day (4mg/kg bid)	4mg/kg/day (2mg/kg bid)	0
10mg/kg/day (5mg/kg bid)	6mg/kg/day (3mg/kg bid)	2mg/kg/day (1mg/kg bid)	0
8mg/kg/day (4mg/kg bid)	4mg/kg/day (2mg/kg bid)	0	–

Maximum LCM dose achieved a	Taper schedule		
	Week 1	Week 2	Week 3
6mg/kg/day (3mg/kg bid)	2mg/kg/day (1mg/kg bid)	0	–
4mg/kg/day (2mg/kg bid)	0	–	–

bid=twice daily; LCM=lacosamide

a Maximum LCM dose achieved is based upon the maximum recommended dose in SP847.

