### Recommended LCM dose reduction (taper) for tablet formulation

Maximum LCM dose achieved a	Taper schedule		
	Week 1	Week 2	Week 3
600mg/day (300mg bid)	400mg/day (200mg bid)	200mg/day (100mg bid)	0
500mg/day (250mg bid)	300mg/day (150mg bid)	100mg/day (50mg bid)	0
400mg/day (200mg bid)	200mg/day (100mg bid)	0	–
300mg/day (150mg bid)	100mg/day (50mg bid)	0	–
200mg/day (100mg bid)	0	–	–

bid=twice daily; LCM=lacosamide

a Maximum LCM dose achieved is based upon the maximum recommended dose in SP847.

At the completion of the study, investigators should discuss treatment options with the subject and/or their parent/legal guardian to best manage the subject's epilepsy. Taper of LCM may not be required for some subjects who complete the study depending on the treatment option selected by the investigator in consultation with the subject and/or parent/legal guardian. These subjects should complete Visit 13/Termination Visit and then complete the Safety Follow-Up telephone contact 28 to 35 days after Visit 13/Termination Visit. The Final Visit is not required for subjects who complete the study and who do not undergo taper of LCM.

Subjects who complete the study and discontinue use of LCM (as determined by the investigator in consultation with the subject and/or parent/legal guardian) should taper LCM gradually as described in Section 4.4.1.3. These subjects should complete Visit 13/Termination Visit, followed by the Final Visit which occurs 2 weeks after the final dose of study medication, and then the Safety Follow-Up telephone contact which occurs 28 to 35 days after the last dose of LCM.

*Clinical Study Protocol, Section 4.4.3. Original text:*

This is an open-label extension study; subjects will not be randomized. Subjects will keep the unique number assigned in the primary study.

*Was revised as follows:*

This is an open-label study; subjects will not be randomized. Subjects who participated in SP847 or other LCM pediatric clinical studies in epilepsy will keep the unique number assigned in the primary study.

Subjects enrolling directly into SP848 without participation in a previous LCM clinical study will be assigned unique numbers for the purpose of study and subject identification, as well as for subject confidentiality. At the Screening Visit, each subject will be assigned the unique identifying number for this study.

*Clinical Study Protocol, Section 4.5 (Expected duration of the study), first sentence. Original text:*

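### The 300 mg/day tablet taper threshold has no weight term, so lighter children on tablets at 6 mg/kg/day or more can stop in one step with no taper drug dispensed

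*Protocol*

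**What the plan says.** Section 4.4.1.3 (revised text in the Amendment 4 log) sets two taper thresholds for subjects who withdraw: at least 6 mg/kg/day on oral solution, or at least "300mg/day (tablet) who withdraw during the study should taper off study medication". The recommended weekly decrements are 4 mg/kg/day and 200 mg/day respectively. The same section caps the dose for both formulations: "The maximum permitted LCM dose in SP848 is 12mg/kg/day or 600mg/day, whichever is lower".

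The Visit 13 text (5.16), the Early Termination Visit text (5.17), footnote n of Table 16-1 and footnote l of Table 16-2 turn the thresholds into a supply rule: lacosamide for taper goes only to subjects who reached one of them. Section 4.1.1 as revised by Amendment 6 repeats the thresholds, and the Amendment 7 and 8 logs do not change them.

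In the recommended tables, the solution row that begins "10mg/kg/day (5mg/kg bid" steps to 6, then 2, then 0 mg/kg/day. The tablet row that begins "200mg/day (100mg bid" goes to 0 in Week 1. A gentler schedule is allowed: "A slower taper of 2mg/kg/day (oral solution [syrup]) or 100mg/day (tablet) is permitted, if medically necessary".

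The investigator and family may choose either formulation. Section 4.4.1.2 lets direct enrollees, from age 4 years, start on tablets. Section 4.1.2 says that the conditions of 4.1.1, including "required office visits for dose increases, concomitant AEDs, and study medication taper) also apply".

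**The concern.** The same daily dose in mg/kg is treated differently by formulation. On solution, any child who has reached 6 mg/kg/day is tapered and supplied for it. On tablets, a light child can be well above 6 mg/kg/day and still fall short of 300 mg/day. Such a child is stopped in one step and given no taper drug at the closing visit.

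What is at stake is patient safety in a narrow group. The protocol lets concomitant antiepileptic drugs be withdrawn to reach lacosamide monotherapy, so some children may have no background drug when they stop. No endpoint, analysis set or estimate depends on this rule.

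**Working it through.** **Inputs from the protocol.** Cap: 12 mg/kg/day or 600 mg/day, whichever is lower. Thresholds: 6 mg/kg/day (solution), 300 mg/day (tablet). Solution decrement: 4 mg/kg/day. Tablet strengths: 50 and 100 mg, given twice daily in equal doses, so daily tablet doses move in 100 mg steps. Body weights are not given; those below are assumptions.

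**The plan's own figure.** (600/70) × 1.4 = 12.0 mg/kg/day, as stated. 600/12 = 50 kg, which matches the 50 kg remark attached to the cap.

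**Where the thresholds agree and part.**
- 300/6 = 50 kg: the only weight at which the two thresholds coincide.
- 300/12 = 25 kg: below this, 300 mg/day exceeds the cap, so a child treated only with tablets cannot reach the tablet threshold.
- 200/6 = 33.3 kg and 200/12 = 16.7 kg: between these weights, 200 mg/day is 6 to 12 mg/kg/day. It meets the solution threshold in mg/kg but not the tablet one.
- 100/6 = 16.7 kg: at or below this, even 100 mg/day is 6 mg/kg/day or more, and no lower equal twice-daily tablet dose exists.
- 400/12 = 33.3 kg: below this, 300 mg/day is the highest tablet dose within the cap.

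**Size of the one-step stop from 200 mg/day.**

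| Weight (kg) | 300 mg/day (mg/kg/day) | 200 mg/day (mg/kg/day) | 200 mg stop ÷ 4 mg/kg/day | 100 mg step (mg/kg/day) |
|---|---|---|---|---|
| 17 | 17.6 (over cap) | 11.8 | 2.9 | 5.9 |
| 20 | 15.0 (over cap) | 10.0 | 2.5 | 5.0 |
| 25 | 12.0 | 8.0 | 2.0 | 4.0 |
| 30 | 10.0 | 6.7 | 1.7 | 3.3 |
| 33 | 9.1 | 6.1 | 1.5 | 3.0 |
| 50 | 6.0 | 4.0 | 1.0 | 2.0 |

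At whole-kilogram weights from 17 to 24, 200 mg/day is the only tablet dose between 6 and 12 mg/kg/day, and it does not qualify. From 25 to 33 kg both 200 and 300 mg/day fall in that range, and only 300 qualifies. A child on 300 mg/day is supplied, but the table's 300-to-100 step is 200/25 = 8.0 mg/kg/day at 25 kg and 200/30 = 6.7 at 30 kg.

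**Does other text repair it?** Section 4.3.3 (Amendment 6) tells everyone who discontinues to taper, and 4.4.1.4 says the same of completers who stop. Both refer back to 4.4.1 or 4.4.1.3, so neither supplies a different threshold.

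**The case against.** Four points have weight.

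**Supply.** A reader might infer that these children can never be stepped down for want of drug. The documents do not say so. Section 4.4.1.3 lets the investigator lower the dose during the study; only increases are tied to office visits. Study drug is dispensed at regular visits and, as applicable, at Unscheduled Visits. A 20 kg child with a planned stop can be moved from 200 to 100 mg/day beforehand. What remains is mainly unplanned withdrawal, and any taper that would begin at Visit 13 or the Early Termination Visit.

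**Origin of the tablet figures.** A reader might also infer that 300 and 200 mg/day are adult figures left unconverted by mistake, because the protocol says that the "scheme, and rate of taper in SP847 were based on adult studies and were adjusted to a mg/kg basis plus 40" per cent. That sentence describes SP847. It does not say how the SP848 tablet rules were derived. Flat tablet amounts run through the whole scheme (start, titration step, taper step), so this reads as a chosen rule and does not contradict the sentence. The point here does not need the conversion.

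**Who is affected.** No weights or formulation counts are given. The planned direct enrollees (100 + 60 = 160, or 206 with Japan's 46) span ages 4 to 17 years and do not estimate the affected group. A child who reached 6 mg/kg/day on solution before switching to tablets does qualify, and a child who continues lacosamide needs no taper. The protocol calls the solution suitable for children, so few light children may be on tablets.

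**Text not seen.** Only the second part of the protocol is at hand. A weight floor for tablets in the first part, or in local Amendments 5.2 and 5.4, cannot be ruled out.

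The taper tables are recommendations and a slower taper is permitted. That leaves the dispensing rule as it stands: permission to taper does not provide the tablets.

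**Conclusion.** The point holds in a limited form. Under 25 kg the tablet threshold cannot be reached within the dose cap. Up to 33.3 kg, 200 mg/day of tablets meets the solution threshold in mg/kg but brings no taper drug and a one-step stop in the recommended table. That stop is 1.5 to 2.9 times the solution decrement at assumed weights of 33 down to 17 kg.

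It applies to children who never reached 6 mg/kg/day on solution and who stop lacosamide without a prior step-down on ordinary study drug. It assumes that no weight floor for tablets exists in the text not seen. The protocol gives no figure for harm from a one-step stop; the yardstick is its own solution rule. This is a narrow safety correction that should be made because it is cheap. It has no bearing on the efficacy or safety analyses.

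**What to change.** In Sections 4.1.1 and 4.4.1.3, the Visit 13 and Early Termination Visit text, footnote n of Table 16-1 and footnote l of Table 16-2, set the tablet threshold at 6 mg/kg/day or more, or 300 mg/day or more, whichever is lower. The Summary should follow where it repeats the figure.

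In the tablet taper table, for children of 33.3 kg or less, recommend the already permitted weekly 100 mg/day steps: 200, 100, 0 and 300, 200, 100, 0. Where no lower equal twice-daily tablet dose exists (100 mg/day at 16.7 kg or less), dispense oral solution for the taper.

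This narrows the disparity and does not remove it. A 100 mg step is still 5.9 mg/kg/day at 17 kg and 5.0 at 20 kg, against 4 on solution. The 33.3 kg limit follows from the 6 mg/kg/day threshold; just above it, a 200 mg step is still 5.9 mg/kg/day at 34 kg.

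Cost: the wording changes, one extra taper week (the Final Visit moves one week later), 7 days × 2 = 14 extra tablets per affected child (50 mg from 200 mg/day, 100 mg from 300 mg/day), and a small supply of solution for the lightest children. No visit is added.

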### **Recommended LCM dose reduction (taper) for oral solution (syrup) formulation**

Maximum LCM dose achieved a	Taper schedule		
	Week 1	Week 2	Week 3
12mg/kg/day (6mg/kg bid)	8mg/kg/day (4mg/kg bid)	4mg/kg/day (2mg/kg bid)	0
10mg/kg/day (5mg/kg bid)	6mg/kg/day (3mg/kg bid)	2mg/kg/day (1mg/kg bid)	0
8mg/kg/day (4mg/kg bid)	4mg/kg/day (2mg/kg bid)	0	–

Maximum LCM dose achieved a	Taper schedule		
	Week 1	Week 2	Week 3
6mg/kg/day (3mg/kg bid)	2mg/kg/day (1mg/kg bid)	0	–
4mg/kg/day (2mg/kg bid)	0	–	–

bid=twice daily; LCM=lacosamide

a Maximum LCM dose achieved is based upon the maximum recommended dose in SP847.

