- j For subjects enrolling from EP0060, these assessments should be completed at Visit 1.
- k Blood samples may be drawn at any time post-dosing with LCM.
- l For female subjects of childbearing potential, serum pregnancy tests will be performed at Visit 1, the Early Termination Visit, and the Final Visit. Urine pregnancy tests will be performed at Visits 2, 3, 4, 5, 6, 7, 8, and 9.
- m The Tanner Stage will be performed only for subjects who are pubescent at Visit 1 or who will enter puberty during the course of the study.
- n Lacosamide for taper will be dispensed only for subjects who achieve a dose of LCM  $\ge 6$ mg/kg/day (oral solution [syrup]) or  $\ge 300$ mg/day (tablet). It is recommended that the LCM dose be tapered gradually in weekly decrements of 4mg/kg/day (oral solution [syrup]) or 200mg/day (tablet). A slower taper of 2mg/kg/day (oral solution [syrup]) or 100mg/day (tablet) is permitted, if medically necessary. In case of an emergency, a faster taper is permitted after discussion with the medical monitor, whenever possible.
- o As applicable
- p For all subjects  $\ge 6$  years of age already enrolled, the "already enrolled" version should be completed at the next clinic visit, and the "since last visit" version should be completed thereafter.
- q The C-SSRS assessment should be completed if the Unscheduled Visit is due to an AE.
- r Ongoing AEs from the primary study will be followed, as well as recording of new AEs during the current study.

*Clinical Study Protocol, Section 16.1 (Table 2 Schedule of study procedures for SP848 [Year 2]). Original table:*

REDACTED COPY

This document cannot be used to support any marketing authorization application and any extensions or variations thereof.

**Table 2.** Schedule of study procedures for SP848 (Year 2)

Study SP848	Year 2								Safety Follow-Up
Visit a	V10	TC b	V11	V12	V13/TermV	ETV c	Unsch Visit d	Final Visit e	TC f
Weeks in study	60		72	84	96				
Concomitant medications	X	X	X	X	X	X	X	X	X
Concomitant AEDs	X	X	X	X	X	X	X	X	X
Physical exam (complete)					X	X		X	
Physical exam (brief)	X		X	X			X		
Neurological exam (complete)					X	X		X	
Neurological exam (brief)	X		X	X			X		
12-lead ECG g			X		X	X	X	X	
Blood pressure and pulse	X		X	X	X	X	X	X	
Body weight and height	X		X	X	X	X	X	X	

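### The taper tables are entered by the maximum LCM dose achieved, which is not reconciled with permitted dose reductions or with the weekly-decrement text, so Week 1 as written can hold or raise the dose

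*Protocol*

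**What the plan says.** The wording is that of Section 4.4.1.3 (All subjects) as set out in the log of Amendment 4. Amendments 5 to 8 log no change to these tables.

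- **Taper rate.** "It is recommended that the dose be tapered gradually in weekly decrements of 4mg/kg/day (oral solution [syrup]) or 200mg/day (tablet) (see tables below". A slower rate is allowed: "A slower taper of 2mg/kg/day (oral solution [syrup]) or 100mg/day (tablet) is permitted, if medically necessary".
- **Row key.** The syrup and tablet tables are both entered by "Maximum LCM dose achieved". The footnote to each reads "Maximum LCM dose achieved is based upon the maximum recommended dose in SP847".
- **Dose reductions.** "The investigator may decrease the dose of LCM to a minimum of 2mg/kg/day", or the corresponding tablet dose. Section 5.18 lets a reduction prompted by an adverse event take effect immediately.
- **Dose increases.** Section 4.4.1.3 limits them to 2 mg/kg/day (syrup) or 100 mg/day (tablet) per week.
- **Threshold for taper supply.** Table 16-1, footnote n: "Lacosamide for taper will be dispensed only for subjects who achieve a dose of LCM" of at least 6 mg/kg/day (syrup) or 300 mg/day (tablet). Table 16-2, footnote l, is worded the same way, and Section 4.4.1.3 also speaks of subjects achieving that dose.

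**The concern.** The tables and the text agree only while the dose being taken equals the row heading. Treatment may last about 2 years, with reductions allowed down to 2 mg/kg/day, so some subjects may withdraw below the highest dose they reached. For them the row heading and the weekly-decrement text can lead to different Week 1 doses, and the text shown does not say which governs.

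The wording does not settle it. Amendment 6 changed the entry-dose rule in Section 4.1.1 from the dose *achieved* in the primary study to the dose *last received*. The taper sentence in the same paragraph kept *achieved*. The formulation-switch paragraph of Section 4.4.1.3 says *current* dose where that is meant. A site therefore has reason to think that *maximum achieved* means something other than the dose in hand.

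At stake is whether sites taper alike, and whether a schedule meant to reduce the dose could, if followed literally, hold or increase it.

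**Working it through.** **Inputs, all from Section 4.4.1.3.** Syrup levels 2, 4, 6, 8, 10 and 12 mg/kg/day; tablet levels 100 to 600 mg/day in steps of 100. Recommended weekly decrement 4 mg/kg/day (200 mg/day). Limit on increases 2 mg/kg/day (100 mg/day) per week.

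**Step 1: the plan's own figure.** Subtracting along each syrup row from its heading:

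| Row heading | Schedule | Weekly steps |
|---|---|---|
| 12 | 8, 4, 0 | 4, 4, 4 |
| 10 | 6, 2, 0 | 4, 4, 2 |
| 8 | 4, 0 | 4, 4 |
| 6 | 2, 0 | 4, 2 |
| 4 | 0 | 4 |

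The stated decrement is reproduced when the current dose equals the row heading; only the last step of the 10 and 6 rows is smaller. The tablet table shows the same pattern with 200 mg/day, and a last step of 100 in the 500 and 300 rows.

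**Step 2: a subject reduced before withdrawal.** Let M be the maximum achieved and r the total reduction, so the current dose is M − r. The table gives Week 1 = M − 4. The change in Week 1 is

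(M − 4) − (M − r) = r − 4 mg/kg/day (tablet: r − 200 mg/day).

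It depends only on r. With M of 6, 8, 10 or 12 (the taper threshold and above) and a current dose of at least 2, there are 2 + 3 + 4 + 5 = 14 pairs:

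| Reduction r, mg/kg/day (mg/day) | Change in Week 1, mg/kg/day (mg/day) | Pairs | Syrup example |
|---|---|---|---|
| 2 (100) | −2 (−100), lowered | 4 | M 12, current 10, Week 1 = 8 |
| 4 (200) | 0, held | 4 | M 12, current 8, Week 1 = 8 |
| 6 (300) | +2 (+100), raised | 3 | M 12, current 6, Week 1 = 8 |
| 8 (400) | +4 (+200), raised | 2 | M 12, current 4, Week 1 = 8 |
| 10 (500) | +6 (+300), raised | 1 | M 12, current 2, Week 1 = 8 |

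Totals: raised 3 + 2 + 1 = 6, held 4, lowered 4. Adding the 4 mg/kg/day row gives one more lowered pair: 6, 4 and 5 of 15. The tablet counts are identical.

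**Step 3: against the limit on increases.** A rise of +2 meets the limit of 2 mg/kg/day per week; +4 and +6 exceed it. So 2 + 1 = 3 of the 6 raised pairs also conflict with that limit.

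**The case against.** The strongest reply is that no one intended a taper to raise a dose. The tables are titled as dose reductions, the schedule is only recommended, and the text they serve speaks of decrements. The literal result sometimes breaks the section's own limit on increases, which is itself evidence against that reading. A careful investigator would taper from the dose in hand. This stands as an argument about intent and limits the practical risk. It does not remove the conflict, because the row key is stated and the shown text never says to depart from it.

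Several stronger readings are tempting but not supported:

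- **That the plan fixes the taper to the highest dose ever reached, so every reduced subject is held or raised.** The word *ever* does not appear, and after a one-step reduction Week 1 is still lower, by the amount of the permitted slower taper. The one reduction described specifically in the shown text, during titration of direct enrollers (Section 5.3), returns the subject to the previous level, normally a single step.
- **That 6 in 14 subjects would be raised.** The 14 pairs are an unweighted grid. The documents give no frequency of reductions.
- **That the footnote cannot apply to subjects outside SP847.** Section 4.4.1 also says that dose selection in this trial rests on the SP847 maximum recommended dose, so the footnote may only explain where the range of rows comes from. It is unclear rather than shown to be wrong.
- **That the primary safety results would be biased.** Events within 30 days after the last dose do count as treatment-emergent, so events in the taper enter those summaries. But nothing shows that reduced subjects are the ones who withdraw, that taper events would be attributed to withdrawal, or that dose records would be distorted; a dose can be recorded as given.

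**Conclusion.** The concern holds as an unreconciled row key. Read as written, the tables contradict the weekly-decrement text for subjects whose dose was reduced by at least 4 mg/kg/day (200 mg/day) below the maximum achieved: held at exactly that reduction, and raised by 2 to 6 mg/kg/day (100 to 300 mg/day) beyond it. They do not do so after a one-step reduction. How many subjects this would affect cannot be derived from the documents, and no statistical result is shown to be affected.

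This rests on two assumptions: that the heading is taken at its word, and that the Amendment 4 wording is still current. The body of Section 4.4.1.3 is in a part of the protocol not shown, and a clarification there cannot be excluded.

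**What to change.** Reconcile the headings of both taper tables, and the *achieve/achieved* threshold wording in Section 4.4.1.3 and in the schedule footnotes (Table 16-1 footnote n, Table 16-2 footnote l), with the weekly-decrement text. One stated reference dose should govern both the threshold and the table row. Which dose that is should be decided by the sponsor's clinicians; the arithmetic above does not choose it.

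Reword the SP847 footnote so that its meaning is clear for subjects who were never in that study. SP847 treated 47 subjects, while up to about 400 may be eligible for SP848.

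The cost is a wording change in the next amendment to two headings, their shared footnote and the threshold sentences. It needs no new data, visits or analyses.
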